6. PROTECTION OF HUMAN SUBJECTS

6.1. Applicable legislation

This is an observational, descriptive, non-interventional study with the main objective of collecting information on patients with genitourinary tumors who present COVID-19 infection, under clinical care and follow-up in the departments of participating centers distributed nationwide.

The study design includes the collection of retrospective and prospective data, promoted by the Spanish Genitourinary Tumors Group (SOGUG) and is considered of public interest. Therefore, in accordance with Order 3470/2009 of Health and Social Affairs (SAS), of December 16, the Sponsor has requested the EPA-AS classification from the AEMPS. This classification has been ratified by the AEMPS on April 23, 2020. In accordance with the same legislation, the participation of any center will be subject to the approval of the Post-authorization Studies Coordination Committee, a favorable opinion from a Clinical Research Ethics Committee accredited in Spain and the approval of the management of each participating center.

Participating in this study does not represent any additional risk for patients because it is a study developed from information recovered from the clinical history and clinical evaluation of patients, all in the context of usual clinical practice and without participation of the patients. patients in any type of intervention or without the modification of the treatment that they would receive if they had not participated in the study.

This protocol will be carried out in accordance with the principles adopted by the 18th World Medical Assembly (Helsinki, 1964) and its subsequent amendments (Fortaleza, 2013), following the rules of good clinical practice and the code of ethics.

6.2. Ethical supervision of clinical research

The study will initially be submitted for evaluation by the **Autonomous CEIm of Galicia**. As detailed in section 6.1, the study will also have the corresponding and applicable authorizations in accordance with the regulations of each center and the guidelines of Order 3470/2009 SAS of December 16.

6.3. Informed consent

All information will be extracted from the medical records of participating patients who have authorized its use by signing the informed consent. All patients included in the prospective part of the study, upon authorization by the competent authorities, must sign an informed consent prior to their inclusion in the study that authorizes the use of the information contained in their medical records.

RETROSPECTIVE PART ONLY: In all cases where it is possible for the patient to sign informed consent, it will be collected. Due to the nature of the study and in order not to generate information bias in those patients with a worse prognosis who have not been able to overcome the disease, exemption from informed consent is contemplated for patients who have died in the retrospective part of the study. study, prior to authorization of the study by the competent authorities.

RETROSPECTIVE PART ONLY: The local Ethics Committee must approve the absence of written authorization by signing the informed consent (as established by local Spanish regulations: SAS

Order 3470/2009). It is possible to dispense with the request for informed consent of patients who have died prior to the authorization of this study by the competent authorities provided that a prior refusal has not been obtained for the signing of the informed consent by of the patient or a revocation thereof. On the other hand, this methodology has been proposed taking into account that:

- There are no studies on the involvement of COVID in patients affected by the disease under study
- The high incidence of fatal cases leads to the need to collect these cases in order not to cause bias in the sample due to relevant loss of patients that generates serious problems of representativeness of the population under study and scientific validity.

For all patients, whether or not they have signed informed consent, the data are included in the study in an anonymized and dissociated form, ensuring that they cannot be associated with any identified or identifiable person. The researcher will assign each patient included in the study a numerical code with which said patient will be identified during the study. The code will not contain personal information and no other data that allows patient identification will be collected during the study. The use of patient data will be subject to a commitment to confidentiality by all personnel participating in the study, including the researcher and his collaborators, data managers, data analysts, and monitors; this should be properly recorded in the patient's medical record, with specific reference to the SOGUG-COVID-19 study. The researchers participating in the study undertake not to identify or carry out re-identification tasks that compromise the anonymity of the patients included in the study.

The data will be recorded using the Electronic Data Capture software owned by MFAR S.L., which is developed and maintained in strict compliance with regulatory standards for electronic digital capture systems for clinical data. All EDC forms are designed according to the eCRF defined by the study protocol.

All database users are uniquely identified by name, all access to the software is over a secure, encrypted connection, and all activities are logged and audited. Only SOGUG (the study sponsor) and MFAR (the CRO with delegated functions) will have access to the data.

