3.2. Secondary objectives

- To evaluate the mortality associated with COVID-19 infection in the population with genitourinary tumors. Percentage of patients alive/dead at discharge.
- To evaluate the rate (percentage) of complications that have required hospital admission and/or ICU treatment.
- Describe the frequency of asymptomatic or minimally symptomatic COVID-19 infections. Percentage of asymptomatic patients or with mild symptoms included in the study.
- Evolution of the oncological disease. Impact/influence of COVID-19 infection on the effectiveness of oncological treatment. Data will be collected on delays/modifications in follow-up or oncological treatment regimens. The average delay time and the number of modifications will be evaluated. Likewise, it is expected to obtain data on time to progression and overall survival of cancer patients, which can be compared with the reference values for each type of tumor pathology.

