4.5. Study sample size

The inclusion of a total of 250 patients with genitourinary tumors presenting with COVID-19 infection is expected, sufficient to respond to the objectives set by the study.

Given the characteristics of the study, the total number of patients cannot be previously calculated accurately, although the inclusion of approximately 250 patients is expected. The planned analysis is the descriptive one of each of the variables. The qualitative variables will be compared with each other using the Chi-square test. Quantitative and qualitative analysis using Student's T analysis or ANOVA. If necessary, the corresponding non-parametric tests will be applied. Survival will be calculated using Kaplan-Meyer curves and curve comparison using Log-Rank.

The Statistical Package for the Social Sciences (SPSS) will be used for statistical analyses. Additional analyzes could be performed with other statistical analysis packages.

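### Entry rules differ by vital status and study part, but mortality and factor comparisons are not planned by part, so pooled mortality depends on an unplanned retrospective/prospective mix and factor comparisons may be biased

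*Combined protocol and SAP*

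**What the plan says.** Section 6.3 (Informed consent) sets three routes into the study.

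- Retrospective, deceased: "exemption from informed consent is contemplated for patients who have died in the retrospective part of the study". The waiver is limited to "patients who have died prior to the authorization of this study by the competent authorities provided that a prior refusal has not been obtained", and the local ethics committee must approve it.
- Retrospective, able to sign: "In all cases where it is possible for the patient to sign informed consent, it will be collected".
- Prospective: every patient "must sign an informed consent prior to their inclusion in the study". Sections 1.2 and 4.8 also confine the waiver to the retrospective part.

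Section 6.3 gives the reason for the waiver: losing fatal cases would harm representativeness and validity.

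On analysis, section 3.2 gives the mortality measure as "Percentage of patients alive/dead at discharge". Section 4.5 says "The planned analysis is the descriptive one of each of the variables", then "The qualitative variables will be compared with each other using the Chi-square test", then t-test or ANOVA, and "Survival will be calculated using Kaplan-Meyer curves and curve comparison using Log-Rank". It mentions no stratification, adjustment or sensitivity analysis by part. Sections 4.2 and 4.5 expect 250 patients without a split between parts. The variable list in section 5.1 has no item for study part or for consent/waiver status.

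**The concern.** A percentage of deaths among included patients estimates mortality only if deaths and survivors enter at the same rate. Here the rates can differ, and in opposite directions. A retrospective death can enter without a signature while a retrospective survivor has to agree, which tends to push that part's figure up. A prospective patient who dies before signing has no stated route in, which tends to push that part's figure down.

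If the two parts are then reported as one figure, two things follow. The figure can move with the mix of parts when nothing about the disease has changed. A pooled value close to the truth can also hide opposite errors in the two parts.

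The factor comparisons serve the main objectives in section 3.1. If a treatment is more common in one part than in the other, the difference in death capture between parts can appear as an association between treatment and death. Admission and ICU percentages could be affected in the same way if sicker patients sign less often; that was not computed.

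**Working it through.** **The plan's own figure.** The 250 cannot be reproduced. Section 4.5 gives no event rate, precision target, alpha or power, and says the number cannot be calculated accurately beforehand. Sampling error for scale, at 20% mortality: 1.96 × √(0.2 × 0.8 / 250) = 5.0 points; with 125 patients, 7.0 points.

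**Inputs.** Only N = 250 comes from the documents. The following are assumed:
- m, true mortality;
- d, fraction of retrospective deaths entered;
- q, fraction of prospective deaths not entered;
- s, fraction of survivors signing, taken as equal in both parts;
- w, retrospective share of included patients.

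**Formulas.**
- Retrospective = m·d / (m·d + (1−m)·s)
- Prospective = m(1−q) / (m(1−q) + (1−m)·s)
- Pooled = w × retrospective + (1−w) × prospective

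**Central case** (m = 0.20, d = 1, q = 0.5, s = 0.7).
- Retrospective: 0.20 / (0.20 + 0.56) = 26.3%.
- Prospective: 0.10 / (0.10 + 0.56) = 15.2%.
- Pooled at w = 0.5: 0.5 × 26.3 + 0.5 × 15.2 = 20.7%. This is close to the true 20% although one part is about 6 points high and the other about 5 points low.

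**Range**, all at m = 0.20:

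| d, q, s | Retrospective | Prospective | Pooled at w = 20/50/80% |
|---|---|---|---|
| 0.8, 0.25, 0.9 | 18.2% | 17.2% | 17.4 / 17.7 / 18.0% |
| 1, 0.25, 0.9 (milder) | 21.7% | 17.2% | 18.1 / 19.5 / 20.8% |
| 1, 0.5, 0.7 (central) | 26.3% | 15.2% | 17.4 / 20.7 / 24.1% |
| 1, 0.7, 0.75 (harsher) | 25.0% | 9.1% | 12.3 / 17.0 / 21.8% |

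The largest departure from 20% in the first three rows is 4.1 points, inside the 5.0-point half-width. In the harsher row it is 7.7 points at w = 20%, outside it. In the first row both parts are low, so even the direction is not fixed.

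The central case at other true rates gives pooled values of 8.6 / 10.5 / 12.4% at m = 10% (half-width 3.7 points) and 26.3 / 30.7 / 35.1% at m = 30% (half-width 5.7 points). These also lie within sampling error.

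**Factor comparison, no true effect.** Take 125 patients per part and central-case mortality.
- Same factor frequency in both parts: mortality is 20.7% with and without the factor, the odds ratio is 1.00, and the test keeps its 5% level.
- Factor in 80% of retrospective and 20% of prospective patients: with the factor 0.8 × 26.3 + 0.2 × 15.2 = 24.1%; without it 0.2 × 26.3 + 0.8 × 15.2 = 17.4%. The odds ratio is (0.241/0.759) / (0.174/0.826) = 1.51.

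False-positive rates of the unstratified chi-square test (no continuity correction, nominal 5%, 200,000 simulated data sets):

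| Case | Factor frequency, retrospective/prospective | Rate |
|---|---|---|
| Central | 80/20 | 26% |
| Central | 70/30 | 14% |
| Central | 60/40 | 7% |
| Milder | 80/20 | 8% |

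A Mantel-Haenszel test stratified by part gives about 5% in these settings.

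**Within one part.** Selection on vital status alone multiplies the odds of death by the same constant in both factor groups, so the odds ratio is preserved. With true rates of 20% and 10% it stays at 2.25. The risk difference is not preserved: the true 10.0 points becomes 13.8 (29.4% − 15.6%) if all deaths and 60% of survivors enter, and 4.8 (9.1% − 4.3%) if 30% of deaths and 75% of survivors enter.

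**The case against.** The study describes itself as descriptive, mortality is a secondary objective, and the waiver is a deliberate and sensible protection against losing fatal cases. No capture rate is documented, and under mild or central assumptions the pooled shift is within sampling error. This stands as to size. It does not remove the point: sampling error is shown by a confidence interval, while this bias is not shown by one and does not shrink with more patients.

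Three stronger readings are tempting, and the documents do not support them.

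- A reader might infer that the planned chi-square comparisons are biased as they stand. They are biased only if the factor's frequency differs between parts or entry depends on the factor. The documents do not report treatment mix by part, and the 26% rate needs an extreme 80/20 contrast.
- A reader might infer, from the classification dated 23 April 2020 and the first centre opening in 3Q 2020, an interval in which deaths could be neither waived nor signed for. Section 6.1 calls the April act a classification and lists the approvals separately. Only an ambiguity is shown: section 6.3 does not say which approval ends the waiver.
- A reader might infer that every early prospective death is lost, or that the parts cannot be separated afterwards. Section 6.3 does not say how soon after diagnosis consent is sought. Study part is probably recoverable, because section 5.1 has a follow-up block timed from inclusion and section 8.2 has sites keep the signed forms. The gap lies in analysis and reporting and need not mean lost data.

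**Conclusion.** The concern holds in limited form. The entry rules differ by vital status and study part, the planned mortality percentage and tests ignore the part, and the mix of parts is not planned. Pooled mortality therefore depends on that mix whenever deaths are captured differently in the two parts. Its bias is of unknown size and direction.

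In the central illustration the parts differ by 11.2 points before rounding (26.3% against 15.2%), while the pooled figure stays within 4.1 points of the truth. Milder inputs give less and harsher ones more. All of this rests on assumed capture rates, with equal signing by survivors in both parts. For factor comparisons the bias is conditional, as set out above. The change is worth making because it is cheap, but the issue does not invalidate the study.

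**What to change.** In sections 4.5 and 5.1:

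1. State the boundary between the retrospective and prospective parts, and which authorization it refers to.
2. Record study part and consent/waiver status for each patient.
3. Report mortality, admission and ICU percentages by part.
4. Stratify factor comparisons by part: Mantel-Haenszel for categorical outcomes, stratified log-rank for survival.
5. Label any pooled figure as mortality among included patients.

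A count of eligible patients not included would help to judge the bias. It is optional and only for centres where ethics approval allows it, because section 6.3 limits extraction to patients who consented or fall under the waiver.

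The cost is two data fields, some added analysis wording, and wider intervals within parts: about 7 points instead of 5 at a 50/50 split. Stratification by part does not correct the selection inside each part, so by-part percentages remain descriptive. The consent rules need not change.

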6.4. Confidentiality

In accordance with the Organic Law on the Protection of Personal Data (Organic Law 3/2018, of December 5, on the Protection of Personal Data and guarantee of digital rights - LOPD), the sponsor guarantees the adoption of the necessary measures to guarantee confidentiality in the processing of personal data.

Only the reporting physicians (principal investigators participating in the study) will know the full name of their patients. No confidential information unnecessary for the intended purposes of the study is collected.

An electronic platform will be used to record data in the Electronic Case Report Form (eCRF). To access the application, users must identify themselves with a username and password strictly for personal use. Each reporting doctor will only have access to the data he/she submitted that is strictly necessary for the work. Any document containing identification data will remain in the center at all times, without being included in the database.

The data will be collected in a research file under the responsibility of the sponsor and will be processed within the framework of the study, ensuring that the sponsor will adopt the relevant

measures to guarantee compliance with current legislation on data protection in all cases. The encrypted data may be transmitted to third parties and other countries, but in no case will it contain information that can directly identify any patient, such as name and surname, initials, address or social security number, among others. If this transfer occurs, it will be for the same study purposes as those described above or only for scientific publications, but always maintaining patient confidentiality in accordance with current legislation.

The database will be examined exclusively by the scientific and medical staff of the sponsor. No personal data or any information that may be related to patients will be included in this database. The database administrator, data manager and monitor (if applicable) will have access to all data that is not linked to any identifiable person.

In data explorations carried out by researchers authorized by the Scientific Committee and in international data transfers to International Registries, if applicable, patients will be identified by a numerical code assigned automatically and randomly by the computer application at the beginning of the registry. each case to maintain the confidentiality of the patient's personal data, as established in the General Data Protection Regulation 2016/679 of the Parliament and of the Council of the European Union (EU) on April 27, 2016.

Access to the personal information of the study subjects will be restricted to the doctor/study collaborators, the health authorities (Spanish Medicines Agency), the Clinical Research Ethics Committee and the personnel authorized by the sponsor, when they need to evaluate the data. and study procedures, but always maintain patient confidentiality in accordance with current legislation.

This evaluation will be carried out in the presence of the main researcher or collaborators, responsible for guaranteeing the confidentiality of the data in the medical records of the study subjects. Only the data collected for the study will be transmitted to third parties, with at least the level of protection of the current legislation, including the transfer of data outside the area of application of the reference legislation.

6.5. Funding source

The study sponsor funds the study according to the guidelines of this protocol. This funding covers all research materials; the cost of registration and control processes in ethics committees and health authorities; the design, maintenance and management of the database; eventual statistical consultations, if necessary; and publication and reporting costs. The financing will, in any case, be independent of the results of the study.

The board of directors/scientific committee of the sponsor guarantees non-interference in the case selection processes, data analysis or in any other process that may affect the results of the study that involve the exploration and presentation of data.

7. REPORTING OF ADVERSE REACTIONS (AR)

In accordance with the provisions of section 8.3 of Order SAS/3470/2009, of December 16, which publishes the guidelines on observational post-authorization studies for medicines for human use, for studies classified as, EPA- AS they are considered prospective monitoring, suspicions of serious adverse reactions that are detected during the course of the study will be notified to the contact point designated by the competent body in matters of pharmacovigilance of the autonomous community where the health professional who carries out his or her activity, notify the case, within a maximum period of 15 calendar days from when you became aware of the suspected adverse reaction.

In the event that the sponsor is a group of professionals (as is the case of SOGUG), you may choose one of the following two options: 1) yellow card to the corresponding autonomous pharmacovigilance center, indicating in observations the name and code of the study from which it comes; or 2) use the online upload through the SINAEM portal of the AEMPS, following the instructions published by the AEMPS (this second option is the recommended one).

For this study, the research team will make notifications of serious adverse reactions to the Sponsor within 24 hours after having become aware of:

MFAR Clinical Research, S.L. [REDACTED]

MFAR will act as recipient of the notifications that it will manage with the Sponsor and after receiving approval from the Sponsor, it will notify the competent bodies of each Community in matters of pharmacovigilance, when appropriate.

The accumulated data on safety aspects (serious adverse events and adverse drug reactions) related to medical products subject to study will be recorded in the eCRF and will be included by the sponsor in the clinical study report, since this study is based on the use secondary data, an expedited report to the sponsor is not required.

In addition to the details specified in the previous paragraph, any relevant safety finding detected during the study will be reported to the AEMPS and the competent bodies of the autonomous communities involved, regardless of the design or type of study.

8. QUALITY GUARANTEE

8.1. Data consistency control

The investigator or designated responsible person is responsible for recording and verifying the accuracy of subject data.

The study will use an online data collection notebook (eCRF). Designated CRO staff will review the data collected by research staff for completeness and accuracy, in accordance with the monitoring plan agreed upon with the Sponsor. Electronic data queries indicating the nature of the findings and requesting clarification for discrepancies and missing values will be created and sent to the research center via an electronic data capture (EDC) system. Designated staff at the investigator's site are required to respond promptly to inquiries and make any necessary changes to the data.

Concomitant treatments and all drug information entered into the database will be coded using the WHO Drug Reference List, which employs the Anatomical Therapeutic Chemistry classification system.

Medical history/current medical conditions and adverse events will be coded using the NCI CTCAE V 5.0 guidelines and the Medical Dictionary for Regulatory Activities Terminology (MedDRA).

Facility staff designated by the investigator will enter the information required by the protocol into the eCRFs as well as the CRO-designated application form.

